**Table 3. End-points for PAPS Pilot study**

Primary End-points
- Improvement of LVEF
- Responders to PVC suppression strategy (delta LVEF $\geq$ 10%)
Secondary End-points
- Successful PVC suppression ( $\downarrow$ PVC burden $\geq$ 80%)
- Composite end-point of adverse events 
 
- Worsening NYHA functional class (I-IV)
 
- Number of HF and cardiac-related Hospital admissions
 
- RFA complications / AAD adverse effects
 
- Cardiovascular death
 

- Composite end-point of arrhythmia burden: 
 
- PVC recurrence (PVC reduction < 80 % after RFA or AAD)
 
- Non-sustained and sustained ventricular arrhythmias
 
- Arrhythmic sudden cardiac death.
 

Subjects that refuse enrollment, will be asked to participate in a PVC-CM registry to follow their response and crossover to different treatment strategies (described above Section A.1)..

We hypothesize that subjects and/or physicians will not object to participate due to the 3-month observation period since most tertiary referral centers have significant procedure wait times for which usually they are scheduled between 8- to 12-weeks after clinical decision of PVC suppression is made. We have involved all participating centers, who agree that this is a common and acceptable scenario during which the observation period proposed could take place. In contrast to other clinical studies where RFA is being compared to placebo, we speculate that randomization of RFA vs. AADs will not be an enrollment limitation since all subjects will undergo a PVC suppression strategy. *This pilot study will allow us to prove feasibility of the PAPS study with the current study design including a 3-month observation period and treatment randomization.*

#### *Rate of spontaneous recovery of CM and PVCs suppression during the 3-month observation period and assess the recurrence of CM and PVCs during a 12-month follow up.*

Due to a known temporal variability of PVC burden over time, it is unclear how often spontaneous variability of PVCs would lead to observing what appears to be spontaneous resolution of PVCs (e.g., without any intervention), which could in theory result in spontaneous improvement of LV dysfunction if CM is secondary to frequent PVCs.

We will assess and compare the PVC burden and LVEF between the time of enrollment and at the end of the 3-month observation period. *This pilot study will allow us to understand the degree and rate of spontaneous improvement of LVEF and reduction of PVCs (control phase) to properly power a large multicenter PAPS study.* Subjects that do not meet both inclusion criteria (LVEF  $\leq 45\%$  and PVC burden  $\geq 10\%$ ) at the end of the observation period will be considered a screen failure, and will be included in a PVC-CM registry if consent has been provided. Based on preliminary data, we believe that less than 10% of subjects will have spontaneous improvement of LVEF  $> 45\%$  and PVC  $< 10\%$ . Registry subjects will have PVC and LVEF assessment every 6 months for the remaining 12 months to understand the recurrence of CM and PVCs (see Section A.1).

#### *Rate of responders to PVC suppression*

Besides improvement in LV systolic function, no study has been designed to demonstrate clinical benefits with either RFA or AADs. Clinical benefits are implied based solely on the improvement of LVEF. Based on prior retrospective and observational studies, the rate of responders (improvement of LVEF) to PVC RFA is estimated at 50-65%. Unfortunately, there is no recent data on antiarrhythmics due to the lack of recent studies. Our preliminary data from the CHF-STAT study demonstrates a response rate of 28% (Preliminary Data Section).

We plan to further identify the rate of responders after PVC suppression by obtaining the following primary end-points: 1) improvement in LVEF (determined by  $\Delta \text{LVEF} = \text{final LVEF} - \text{baseline LVEF}$ ) and 2) “responders” to PVC suppression (defined as change in LVEF  $\geq 10\%$ ). In addition, we will obtain QOL and NYHA functional class questionnaires (secondary end-point described above). Each subject will serve as its own control, since all data obtained will be compared between the end of 3-month observation period (control phase - prior to randomization) vs. 3-month after PVC suppression strategy, regardless of treatment randomization (RFA and AAD). We hypothesize that a PVC suppression strategy (RFA or AAD) is better than optimal HF medical therapy alone to improve LV function, HF symptoms, heart failure admissions, and avoid the need for defibrillator. *The PAPS pilot study will help us determine the rate of responders to PVC suppression strategy in order to properly estimate sample size and power the large randomized PAPS study.*

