**A. Study Population and Eligibility**

This is a prospective randomized pilot study including between 36-39 subjects with cardiomyopathy (CM) and high PVC burden with a likely diagnosis of PVC-CM, where all subjects will be assigned to a 1:1 random allocation to one of two un-blinded PVC suppression groups: 1) PVC radiofrequency ablation (RFA) vs. 2) antiarrhythmic drugs (AADs).

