#### **E. Primary and secondary outcome measures.**

*The outcomes are divided in primary and secondary end-points (Table 3).*

*The primary end-points will consist of:*

1. *Improvement of LVEF after PVC suppression at 12-month follow-up.* This is chosen as primary-end point due to the known prognostic value of LVEF. The lower the LVEF, the higher the risk of sudden cardiac death and heart failure. This will compare the overall improvement or change in LVEF between RFA and AAD groups. This end-point will support that either RFA or AADs have an overall better outcome due to significant improvement of LV function with potential impact on morbidity and mortality associated with PVC-CM.

2. *Responders to PVC suppression strategy at 12-month follow-up* (See rationale under Section “Definitions” in 3rd paragraph of Aim 2). Assessment of the number of responders (delta LVEF  $\geq$  10%) after PVC suppression strategies (RFA or AADs) will assess the effectiveness of RFA and AADs to reverse or improve cardiomyopathy induced by frequent PVCs. Evidence that either RFA or AADs is superior to improve or even reverse LV dysfunction in subjects with high burden PVCs could have significant impact of morbidity and mortality including future heart failure and ventricular arrhythmias, and also may avoid ICD implantation.

*The secondary end-points will consist of:*

1. *Efficacy of RFA vs AADs groups to achieve successful PVC suppression at 12-month follow-up, defined as a reduction of PVC burden  $\geq$ 80% (regardless of LVEF change). Understanding the success rate of PVC suppression between RFA and AADs will help better determine the best treatment to those subjects with high PVC burden.*

2. *Composite end-point of adverse events at 12-month follow-up, including worsening in NYHA functional class (I-IV), number of HF and cardiac-related admissions, RFA complications and AAD adverse effects and cardiovascular death.*

This adverse event composite end-point is chosen to understand the overall complications and adverse effects/events related to RFA and AADs. Worsening of NYHA functional class will be defined as when/if the subject’s functional status worsens by one NYHA class. Hospital admissions will be defined as any visit to ED or hospital admissions related only to a cardiovascular event such as heart failure, angina, pre/syncope and palpitations.

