#### Sample size justification.

*This has been estimated solely on primary end-point of improvement in LV ejection fraction after PVC suppression. We are planning to compare the improvement in LVEF between PVC suppression strategies (RFA vs. AADs groups). Due to the multiple random effects, a simulation study was conducted to estimate the number of subjects required for this study. Specifically, data was simulated according to a linear mixed-effects model with an unstructured error structure with a random site effect. It was assumed that subjects would have a LVEF level of 25% (SD=5%) in each of the groups at baseline and LVEF levels of 40% and 35% (SD=10%) in the RFA and AAD groups at 12 months, respectively. A within subject correlation of 0.25 was assumed along with an inter-site standard-deviation of 1%. *This model was fit assuming that, on average, 10% of the subjects would drop out randomly.* Approximately 140 total subjects (70 per group) should be enrolled to reject the null hypothesis that the mean LVEF between RFA and AAD groups are equal with probability (power) 0.8 and Type I error probability of 0.05. *As a pilot study we have determined the need to enroll at least 20% (30 subjects) of preliminary sample size estimation to understand feasibility and key aspects of subject enrollment, randomization and retention to properly power a large-scale randomized PAPS study. Sample size is increased by 15% (6-9 additional subjects, 36-39 subjects total – between 19-20 subjects in each treatment group) to take into account possible spontaneous improvement of LV dysfunction during the 3-month observation period between treatment strategies.**

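### Primary end-point 1 is a change in LVEF compared between arms with no baseline adjustment named; adjusting for pre-treatment LVEF is a modest, nearly cost-free improvement

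*Combined protocol and SAP*

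**What the plan says.** Section F (Rate of responders to PVC suppression) sets out the plan as "obtaining the following primary end-points: 1) improvement in LVEF (determined by" final LVEF less baseline LVEF. Of the same end-point, Section E and the Synopsis say: "This will compare the overall improvement or change in LVEF between RFA and AAD groups".

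Section A states that "all subjects will be assigned to a 1:1 random allocation to one of two un-blinded PVC suppression groups". Under Definitions and Avoidance of bias, randomisation is stratified on PVC burden above or below 20% and on nothing else.

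Section I describes baseline comparisons by Fisher and Wilcoxon tests, unadjusted relative risks, and an extended relative-risk model that looks at baseline PVC burden. It gives no model for continuous LVEF and does not mention baseline LVEF as a covariate.

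The Sample size justification does describe a linear mixed-effects model with unstructured errors and a random site effect, but only as the basis of the simulation. It does not say whether the arms share a baseline mean or which contrast is tested.

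**The concern.** A between-arm difference in raw change treats the regression slope of final on baseline LVEF as 1. If the true slope is lower, an arm that starts higher by chance is penalised too much, and subtracting baseline adds noise that adjustment would avoid.

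Two things are at stake. One is precision, in the pilot and in the full trial that the pilot is meant to help power. The other is exposure to chance imbalance in a pilot of 36 to 39 subjects whose randomisation does nothing to balance LVEF. Section I tests for baseline differences but does not say what follows if one appears.

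**Working it through.** **Inputs** (all from the Sample size justification)
- Baseline: "It was assumed that subjects would have a LVEF level of 25% (SD=5%) in each of the groups at baseline".
- 12 months: "LVEF levels of 40% and 35% (SD=10%) in the RFA and AAD groups at 12 months", so the target difference is 5 points.
- Correlation: "A within subject correlation of 0.25 was assumed along with an inter-site standard-deviation of 1" per cent.
- Error rates: "with probability (power) 0.8 and Type I error probability of 0.05"; sidedness is not stated.
- Dropout: "on average, 10% of the subjects would drop out randomly".

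**1. Reproduce the plan's 140.** Var(change) = 5² + 10² − 2 × 0.25 × 5 × 10 = 100, so SD = 10. Evaluable n per arm = 2 × 100 × (1.96 + 0.842)² / 5² = 62.8, rounded to 63. Then 63 / 0.9 = 70 per arm, 140 in total: an exact match for a two-sided test. A one-sided test gives 50, then 56 per arm, or 112. The 12-month value alone also has SD 10 and gives the same 140, so this figure does not reveal which contrast was simulated.

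**2. Slope.** Correlation × SD(12 months) / SD(baseline) = 0.25 × 10 / 5 = 0.5. An unadjusted change comparison imposes 1.

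**3. Adjusted variance.** 10² × (1 − 0.25²) = 93.75 (SD 9.68), which is 6.25% below 100. Evaluable n per arm = 2 × 93.75 × (1.96 + 0.842)² / 5² = 58.9, rounded to 59. After dropout this is 66 per arm, 132 in total. At 63 evaluable per arm, power is 0.826 against 0.801 (normal approximation). A simulation at 140 subjects with 13 sites and 10% random dropout (20,000 runs) gave 0.813 adjusted, 0.793 for change and 0.788 for the 12-month value. Bias was close to zero for both the adjusted and the change comparison.

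**4. Dependence on the correlation and on pilot size.** With SDs 5 and 10, Var(change) = 125 − 100ρ and Var(adjusted) = 100(1 − ρ²). Estimating the slope with n per arm multiplies the adjusted variance by 1 + 1/(2n − 4); at n = 18 that is 33/32 = 1.031.

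| Correlation | Change | Adjusted | Ratio, large sample | Ratio, 18 per arm |
|---|---|---|---|---|
| 0 | 125 | 100 | 0.800 | 0.825 |
| 0.25 | 100 | 93.75 | 0.938 | 0.967 |
| 0.35 | 90 | 87.75 | 0.975 | 1.005 |
| 0.4 | 85 | 84 | 0.988 | 1.019 |
| 0.5 | 75 | 75 | 1.000 | 1.031 |
| 0.6 | 65 | 64 | 0.985 | 1.015 |
| 0.8 | 45 | 36 | 0.800 | 0.825 |

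A separate simulation of 100,000 trials with 18 per arm agrees: at correlation 0.25 the standard errors are 3.34 (change) and 3.29 (adjusted).

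**5. Chance imbalance in the pilot.** With 36 subjects (18 per arm), the standard error of the baseline difference is 5 × √(2/18) = 1.67 points, and the 95% limit is 1.96 × 1.67 = 3.3. Given an imbalance, the change-score difference moves by (0.5 − 1) times it: about 0.8 points at one standard error and 1.6 at the 95% limit. The standard error of the treatment difference itself is 10 × √(2/18) = 3.33.

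**The case against.** The strongest reply is that the plan defines an outcome variable and never declares an estimator. Taking change as the outcome does not force a slope of 1, because ANCOVA on change with baseline as covariate gives the same treatment effect as ANCOVA on the 12-month value. The only inferential wording, in the Sample size justification, refers to equality of mean LVEF and to a mixed model. This stands: a reader might infer that the protocol commits to an unadjusted change-score test, and the text does not go that far. Nor does the mixed model close the gap. With unconstrained baseline means and complete data, its group-by-time contrast is the change-score difference; only a version with a common baseline mean behaves like ANCOVA.

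A reader might also infer that the change score biases the trial. It does not: over randomisation it is unbiased. The 1.6-point shift is a limit case, and even that is about half of the pilot's standard error.

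Third, at pilot size adjustment is not a guaranteed gain, as the last column of the table shows. That also stands.

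Finally, the pilot's aim is feasibility, and the Data Sharing Plan says its data are not meant to settle which strategy is better. This limits the consequence. The LVEF comparison is nevertheless listed as a primary end-point, and settling the estimator in advance removes a choice after the data are seen.

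**Conclusion.** The point holds as a modest improvement. The plan compares change in LVEF between arms without naming any baseline adjustment or any model for continuous LVEF. Under its own assumptions, an unadjusted change comparison gains nothing over the 12-month value.

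In the full trial, adjustment is worth 6.25% of variance: 8 of 140 subjects, or 2 to 2.5 points of power. In the pilot, the main reason to adjust is protection against chance imbalance in LVEF; the average precision gain at correlation 0.25 is about 3% of variance.

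These figures rest on SDs of 5 and 10 and a correlation of 0.25, none of which is yet confirmed. In large samples with these SDs, adjustment is never less precise and ties only at correlation 0.5. It does not follow that 140 is an error: it reproduces exactly for the unadjusted comparison.

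**What to change.** In Sections F and I, state that the between-arm comparison of end-point 1 is adjusted for pre-treatment LVEF. This can be ANCOVA on change, ANCOVA on 12-month LVEF, or the mixed model of the Sample size justification with a common baseline mean. Report the adjusted mean difference with its 95% CI. Change can remain the reported outcome, and the responder end-point is unaffected.

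Name which echocardiogram is the baseline for this comparison. The enrolment echocardiogram may be up to 150 days old at enrolment, while Observation Visit 3 provides one at week 12. Section F uses the end of the observation period for its pre/post comparison but does not fix the baseline for the 12-month comparison between arms.

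The cost is wording only, since Table 2 already schedules these echocardiograms. The one statistical downside is a loss of up to about 3% of variance at pilot size if the true correlation is near 0.5.

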- 2) The rate of responders (defined as improvement of LVEF  $\geq$  10% points) with HF medical therapy alone during observation period will be less than 15% *in subjects with CM associated with frequent PVCs*. In contrast to HF medical therapy alone, RFA and AADs will have a responder rate of *at least 35% in the same population*. *Furthermore, RFA will have a greater 1-year response rate when compared to AAD therapy.*
- 3) *RFA will have a lower rate of composite adverse events (worsening NYHA class, HF admission, treatment side effects & complications, and death), arrhythmia burden and a better long-term tolerance than AADs.*
- 4) The prevalence of CM (LVEF  $\leq$  45%) and frequent PVCs ( $\geq$ 10% burden) is largely under recognized in subjects undergoing ambulatory ECG Holters (Part II).

**Methods.** To test our hypotheses, we propose: 1) a clinical pilot study to prove the feasibility of a large-scale multicenter clinical trial (PAPS study) of subjects with probable PVC-CM, and 2) screen near 20,000 consecutive ambulatory ECG Holter monitors of all participating centers to identify all subjects with probable diagnosis of PVC-CM (PVC burden  $\geq$ 10% and LVEF  $\leq$ 45%). The clinical pilot study will enroll between 36-39 subjects with frequent PVCs (burden  $\geq$ 10%) and CM (LVEF  $\leq$ 45%) and randomize them to either: 1) RFA or 2) AADs. Prior to treatment, a baseline cardiac MR will be performed if clinically indicated and be allowed a 3-month observation period. To assess the effects of PVC suppression, we plan to compare changes in LV function, rate of responders (defined above), PVC burden/arrhythmias and clinical/functional status (QOL, HF symptoms and admissions, NYHA class) and adverse events between observation period both PVC suppression strategies (RFA or AAD).

To identify the best PVC suppression strategy, we will perform similar comparisons between RFA and AAD treatment groups during a 12-month follow up using a Prospective Randomized Open, Blinded End-point (PROBE) study design. The treatment regimens will be compared in an intention-to-treat analysis.

Our study is *unique due to its multidisciplinary approach and design* including: 1) observation/control period that allows us to assess for spontaneous improvement of PVCs and/or CM, and 2) active treatment to all subjects, which will allow for easier subject enrollment and retention with minimal drop out.

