iii. *Observation – Visit 3.* Similar to Visit 1, appropriate data collection forms should be used to collect current medical therapy, NYHA functional class and Minnesota HF quality of life questionnaire (QOL). 12-lead ECG should be obtained if clinically indicated. Transthoracic echocardiogram should be performed to assess LVEF and a copy mailed to the Echo Core laboratory led by [name] III, M.D. The local PI and designated site staff will be able to log in to iRhythm's ZioReports to obtain the Zio Patch report that should include a 2-week PVC burden.

[figure not shown]
If PVC burden remains  $\geq 10\%$  and LVEF  $\leq 45\%$ , then the subject will either initiate antiarrhythmic drugs or undergo RFA procedure (see Section C: Description of the intervention/treatment) and will continue on protocol as scheduled. However, if these criteria are no longer met, the subject is considered a screen failure and is withdrawn from the study. In such a case, the treatment decision is solely at the discretion of the electrophysiologist caring for subject. Nevertheless, this subject will be included in a PVC-CM registry if consent was provided (described above Section A.1).

i) *Treatment – Visit 1.* This is considered the baseline visit where PVC suppression strategy assignment is initiated (either RFA or AADs). If the subject is randomized to RFA, we will request that sites complete the RFA data collection form which includes information during the RFA procedure as well as recovery, complications and hospital stay. EPS will be performed on their baseline medications, except for antiarrhythmic drugs class II (beta blockers) which will be held at least 5 half-lives prior to procedure. Beta blockers should be resumed after RFA.

iv. However, subjects randomized to AADs can have this visit combined with Observation-Visit 3. In addition, subjects in the antiarrhythmic (AAD group) will require a baseline TSH and LFTs (AST only) if amiodarone is chosen.

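### The own-control comparison keeps only subjects whose LVEF is still at or below 45% at Week 12, which can favour suppression with no effect, materially so if many enter above about 35%

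*Combined protocol and SAP*

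**What the plan says.** Specific Aims, Hypothesis 2, predicts that the responder rate "with HF medical therapy alone during observation period will be less than 15"% and that RFA and AADs will reach at least 35% in the same population. A responder is a gain of 10 LVEF points. The Definitions paragraph says more than 10 and other sections say 10 or more; this makes no practical difference here.

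Section F, Rate of responders to PVC suppression, sets out the before-after comparison: "Each subject will serve as its own control, since all data obtained will be compared between the end of 3-month observation period" and 3 months after suppression, with both arms pooled. It goes on to hypothesise that suppression is better than optimal heart-failure therapy alone.

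Entry requires LVEF at or below 45% and PVC burden of at least 10%. Section B, Observation – Visit 3, applies the same limits again at Week 12: "However, if these criteria are no longer met, the subject is considered a screen failure and is withdrawn from the study". Under section A.1 such subjects are then followed, with consent, only by chart review at 6 and 12 months.

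The part of section F on spontaneous recovery separately plans to compare enrolment with Week 12 and does not restrict that to continuers. No section names the analysis set for either responder rate, and section I gives no method for the before-after comparison.

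**The concern.** A subject withdrawn at Week 12 has no study echo 3 months after suppression, so any paired comparison is confined to continuers. Two things follow.

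- **A one-sided cap.** A continuer's gain during observation cannot take LVEF past 45%. The gain during treatment has no such limit.
- **Regression to the mean.** The reading used to select continuers is also the starting point of their treatment change. Selecting low readings makes the next change look larger.

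Both push towards suppression. A third problem is separate from the gate. A Week-12 versus 3-month contrast has no concurrent control, and section B lets heart-failure therapy be titrated, so any continuing improvement is credited to suppression.

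At stake is the reading of Hypothesis 2, and the responder and spontaneous-improvement rates that section F says will help power the full trial.

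**Working it through.** **1. The plan's own figure.** Sample size justification assumes "LVEF level of 25% (SD=5%) in each of the groups at baseline", "LVEF levels of 40% and 35% (SD=10%) in the RFA and AAD groups at 12 months", and "A within subject correlation of 0.25 was assumed", "with probability (power) 0.8 and Type I error probability of 0.05", with 10% dropout. Sidedness is not stated; two-sided is assumed.

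- SD of change = √(5² + 10² − 2 × 0.25 × 5 × 10) = √100 = 10.
- n per arm = 2 × (1.960 + 0.842)² × 10² / 5² = 62.8, so 63. Then 63 / 0.9 = 70 per arm, 140 in total.

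The 140 reproduces. Adding the "inter-site standard-deviation of 1"% gives 144. This calculation concerns the randomised contrast. The documents give no figure for the before-after comparison.

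**2. The cap.** Let E be the entry reading and W the Week-12 reading. A continuer has W ≤ 45, so W − E ≥ 10 requires E ≤ 35. A continuer who entered above 35% cannot be an observation responder. The share of enrolled subjects with E above 35, for normal readings truncated at 45, is [Φ((45−μ)/σ) − Φ((35−μ)/σ)] / Φ((45−μ)/σ):

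- mean 25, SD 5 (plan): about 2%
- mean 35, SD 8 (assumed): (0.894 − 0.500) / 0.894 = 44%
- mean 38, SD 8 (assumed): (0.809 − 0.354) / 0.809 = 56%

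**3. Null simulation, drifting LVEF.** There is no suppression effect. Assumptions: true LVEF drifts +3 (SD 6) in each of the two periods, and echo error has SD 3 to 5. Subjects are enrolled if the first reading is ≤ 45 and kept if the second is ≤ 45. The PVC criterion is not modelled. Ranges run over the two echo errors.

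| Entry mean / SD | Observation responders, continuers | Treatment responders, continuers | Observation responders, all enrolled |
|---|---|---|---|
| 25 / 5 (plan) | 15-20% | 17-23% | – |
| 35 / 8 (assumed) | 10-14% | 18-25% | 17.8-24.5% |
| 38 / 6 (assumed) | 6-11% | 19-26% | 18.2-25.5% |

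At mean 35, 54-55% of observation responders are removed. Counting all enrolled subjects nearly closes the gap (17.8% against 18.1% at echo error 3).

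**4. A second null model.** Three readings share a subject effect, with correlation 0.25 unless stated.

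- 25 / 5, no trend: 5.1% against 5.1%; 0.1% of observation responders removed.
- 35 / 8, no trend: 12.2% against 17.0%; 35% removed. The continuers' mean change is 0.0 in observation and +1.1 in treatment. With all enrolled as denominator the observation rate is 17.0%.
- 38 / 8, no trend: 10.7% against 18.3%; 52% removed; treatment change +1.8. All enrolled: 18.8%.
- 38 / 8, +3 per period: 14.8% against 31.4%, close to the hypothesised 15% and 35%. All enrolled: 28.7%, so a small gap remains.
- At 38 / 8 with +3 per period, higher correlation shrinks the gap: 12.6% against 24.0% at 0.5, and 7.6% against 12.9% at 0.75.

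**5. The Week-12 versus 3-month contrast taken literally.** The plan names no test, so a paired t-test with 36 enrolled is assumed (nominal 0.025 in favour of suppression). Under the step 3 model with no drift and echo error 4, the false-positive rate is 0.026, 0.04 and 0.056 at entry means 25, 35 and 38. Under the step 4 model with no trend it is 0.026, 0.098 and 0.182. With +3 drift the step 3 model gives about 0.5-0.7, even at mean 25 where the gate hardly acts.

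**6. An illustration of the denominator.** Suppose 36 enrol and 6 are withdrawn at Week 12. If 3 of the 30 continuers are observation responders, the rate is 3/30 = 10%. If 3 of the 6 withdrawn also gained 10 points, the all-enrolled rate is 6/36 = 17%. The first supports the under-15% hypothesis and the second does not.

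**The case against.** A reader might infer that observation responders are removed wholesale by design. They are not: only those who cross 45% leave, and at the plan's own baseline (25%, SD 5) the step 4 model removes practically none. The larger figures need entry means that no section states. This stands and limits the size. It does not dispose of the point, because eligibility runs to 45% and the Enrollment section seeks mild as well as severe cardiomyopathy.

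A reader might also infer that the observation rate in Hypothesis 2 must be computed in continuers. The spontaneous-recovery text allows all enrolled subjects, and on that denominator the gap nearly closes. This stands too, but the text permits that rate without requiring it, and it cannot repair a paired contrast.

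Larger false-positive rates (0.04-0.05, about 0.15 and about 0.26 at means 25, 35 and 38) can be produced by a paired t-test of treatment change minus observation change under equal drift. No section plans that test. Equal drift is also doubtful: the entry echo may be up to 150 days old and therapy may be titrated, so observation gains could be larger. With +5 or +6 in observation against +3 in treatment, the mean-35 rate falls to 0.05 or 0.03. Those rates are therefore not claimed here.

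Finally, Aim 1 is feasibility, the primary endpoints compare randomised arms, and the Data Sharing Plan disclaims conclusions about the benefits of the strategies. That limits the consequence.

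**Conclusion.** The point holds, conditionally on who enrols. It follows from the documents that the own-control comparison is confined to subjects who pass the Week-12 criteria, that its pre-treatment value is the gated reading, and that a continuer who entered above 35% cannot have been an observation responder. Suppression can therefore look better than heart-failure therapy alone with no effect.

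The size rests on assumptions about entry LVEF, drift, echo error and within-subject correlation. It is small at the planning values and material if many enter above about 35% (10-14% against 18-25% under the null at mean 35, SD 8). If LVEF is drifting upwards, the missing control for time is the larger weakness of the literal Week-12 versus 3-month contrast.

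It would be wrong to conclude that the randomised RFA-versus-AAD comparison is biased by this. The same criteria apply to both arms, and that comparison does not use the before-after contrast.

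**What to change.** - **Denominator.** For Hypothesis 2, compute the observation-period responder rate in all enrolled subjects with a Week-12 echo, counting Week-12 withdrawals by their observed change. That echo is obtained before withdrawal, so no new data are needed.
- **Model.** If LVEF change is modelled, use all echoes of all enrolled subjects and include observed PVC burden, because withdrawal depends on it as well as on LVEF. Missing at random is not plausible with LVEF alone. Record whether the site or the core-laboratory LVEF decided continuation, since the documents do not say, and include the one that did.
- **Label.** Present the before-after contrast in continuers as descriptive, with a note on regression to the mean and background trend, and not as evidence that suppression beats heart-failure therapy.

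The cost is analysis-plan wording, a little more analysis, and a less favourable contrast. The withdrawal rule itself need not change for this purpose.
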